6.5.5.1.2 Adverse event reporting period

The period for recording AEs in the eCRF, begins upon receiving the first dose of investigational medication until EOS. All AEs must be recorded on specific AE forms of the eCRF. AEs that are reported from start of infusion and over the next 24 hours will be considered infusion related, and they will be analyzed separately. The investigator should report the actual event, e.g. rash, hypotension.

Monitoring of suspicion of infections is requested throughout the study. Type of investigation, specimen, result, and pathogen identified will be captured in the eCRF. Any entry of new infection (assessed as serious and clinical suspicion of infections caused by pathogens potentially favored by IFN- γ neutralizations) in the eCRF will prompt to complete "infection log" to collect information regarding pathogen and specimen from which a pathogen has been isolated.

Figure 2 Overview of non-serious AE and SAE reporting period

6.5.5.1.3 Eliciting and recording adverse event information

The investigator is to record all directly observed AEs, and all AEs spontaneously reported by the patient, in the eCRF using concise medical terminology. In addition, each patient will be questioned about AEs at each clinic visit following initiation of treatment

When possible and appropriate, a diagnosis rather than individual signs and symptoms shall be recorded. The investigator is responsible for obtaining sufficient information to determine seriousness, causality, and outcome of each AE.

Severity assessment

The investigator will use the adjectives MILD, MODERATE, or SEVERE to describe the maximum severity of the AE. For the purpose of consistency, these severity grades are defined as follows:

MILD	Does not interfere with patient's usual function
MODERATE	Interferes to some extent with patient's usual function
SEVERE	Interferes significantly with patient's usual function

Note the distinction between the gravity (seriousness) and the severity of an AE. **Severe** is a measure of intensity; thus, a **severe** reaction is not necessarily a **serious** reaction. For example, a headache may be severe in intensity, but would not be classified as serious unless it met one of the criteria for serious events listed above.

If the intensity of an AE worsens during the study, only the worst intensity should be reported on the AE page. If the AE lessens in intensity, no change in the severity is required.

Events occurring during the screening period (i.e. after signature of informed consent up to IMP initiation) are considered medical history. If it worsens after IMP initiation or during the follow-up period, an AE form must be entered with the appropriated intensity.

Causality assessment

For each AE, the investigator must make a causality assessment to determine if there is a reasonable possibility that the IMP caused the AE. The AE is assessed as related or not related to

the IMP. The determination of the likelihood that the IMP caused the AE will be provided by an investigator who is a qualified physician.

- Related

An AE that follows a reasonable temporal sequence from administration of the IMP (including the course after withdrawal of the IMP), or for which possible involvement of the IMP cannot be ruled out, although factors other than the IMP, such as underlying diseases, complications, concomitant drugs, and concurrent treatments, may also be responsible.

- Unrelated

An AE that does not follow a reasonable temporal sequence from administration of the IMP and/or that can reasonably be explained by other factors, such as underlying diseases, complications, concomitant drugs, and concurrent treatments.

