6.5.5.1.5 Follow-up of unresolved adverse events

All serious and non-serious AEs assessed by the investigator as related to the IMP should be followed until they are resolved or the investigator assesses them as chronic or stable, or the patient's participation in the study ends, i.e., until the EOS visit. How to report changes in an ongoing AE during a patient's participation in the study is described in the eCRF instructions.

In addition, all serious and non-serious AEs assessed by the investigator as related to the IMP should continue to be followed until they resolve or until the investigator assesses them as "chronic" or "stable", even after the patient's participation in the study is over, but without further recordings into the eCRF.

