#### **6.10.1. Adverse Events**

Detailed information on AEs occurring after the first dose of investigational medication until EOS including adverse event term, start data and time, end date and time, outcome, maximum severity, relationship to IMP and potential causative factors, whether the AE caused study discontinuation, answer indicating whether the event is a SAE, and criteria met for SAE will be collected in the CRF. All AE records collected will be included in the analysis. Adverse event terms will be standardized using the latest updated English version of MedDRA.

An adverse event will be considered treatment-emergent if the start date and time of the event are equal to or later than the date and time of first infusion (otherwise pre-treatment event). For determination of treatment-emergent AEs with presence of missing data, please refer to [Section 6.2.1](#).

Besides secondary analyses described in [Section 6.8.1](#), the overall incidence of TEAEs related to study drug (non-serious related AEs) and serious TEAEs related to study drug will be summarized at event level and subject level by SOCs and PTs.

In addition, the incidence of treatment-emergent AEs and treatment-emergent SAEs will be tabulated by SOCs and PTs based on maximum severity.

The overall incidence of all AEs, treatment-emergent AEs, treatment-emergent SAEs, severe treatment-emergent AEs, infusion-related AEs, infection-related AEs, treatment-emergent AEs related to study drug, severe treatment-emergent AEs related to study drug, all SAEs, treatment-emergent SAEs, serious treatment-emergent AEs related to study drug, infusion-related SAEs, infection-related SAEs, AE leading to treatment temporarily interrupted related to study drug, AEs leading to treatment permanently discontinued related to study drug, AEs leading to study withdrawal and AEs leading to death at event level and subject level will be tabulated in a summary table. In addition, AEs occurred prior to HSCT and after HSCT will be similarly tabulated.

For all treatment-emergent SAEs, the incidence will be tabulated at event level and subject level by criteria met in a summary table.

Listings will be provided for all AEs, SAEs, AEs resulting in study discontinuation, AEs resulting in death, infusion-related AEs, infection-related AEs, and AEs leading to treatment temporarily interrupted/treatment permanently discontinued related to study drug.

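### Only the worst intensity of an AE is kept and its worsening is not dated, so the SAP's severe-AE rows before and after HSCT cannot be filled reliably for AEs that span the transplant

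*Protocol*

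**What the plan says.** **Recording.** Protocol 6.5.5.1.3 makes the grade a property of the whole event: "The investigator will use the adjectives MILD, MODERATE, or SEVERE to describe the maximum severity of the AE". If the event gets worse, "If the intensity of an AE worsens during the study, only the worst intensity should be reported on the AE page". If it eases, the grade need not be lowered. Protocol 6.5.5.1.2 runs AE recording from first dose to EOS, and Protocol 6.1 places EOS one year after HSCT, at most 18 months after first dose. The recorded grade can therefore come from the transplant period.

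**Fields.** SAP 6.10.1 lists the AE term, a start, and then "end date and time, outcome, maximum severity, relationship to IMP and potential causative factors", followed by study discontinuation and seriousness items. No date of a change in intensity is listed.

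**Tabulation.** The overview table in SAP 6.10.1 includes "severe treatment-emergent AEs, infusion-related AEs, infection-related AEs, treatment-emergent AEs related to study drug, severe treatment-emergent AEs related to study drug". The SAP then adds: "In addition, AEs occurred prior to HSCT and after HSCT will be similarly tabulated". It gives no rule for an AE that starts before HSCT and continues past it. The only dating rule in that section concerns treatment emergence, which it decides by comparing the start of the AE with the first infusion.

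**Deferred detail.** Protocol 6.5.5.1.5 states: "How to report changes in an ongoing AE during a patient's participation in the study is described in the eCRF instructions". Those instructions are not part of the two documents.

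**The concern.** A table of severity by period needs to know in which period the severity occurred. The listed fields say when an event began and ended and how bad it became, but not when it became that bad. For an AE lying wholly on one side of HSCT this does not matter. For an AE that crosses HSCT, the peak grade may belong to either side.

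Such AEs are foreseeable. Expected progression to HSCT is an inclusion criterion (Protocol 6.3.1), and Protocol 4.1.1.3.3 reports that SAEs in another emapalumab study included events typical of HSCT. The trial has no control arm, so the split by HSCT is the planned AE tabulation that separates safety on emapalumab from safety after transplant. If post-transplant worsening enters the pre-HSCT severe rows, emapalumab looks worse than it was and the post-transplant period looks better. Treatment-emergent AEs are secondary endpoints supporting the primary, safety objective (Protocol 5.1.2).

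**Working it through.** The plan states no figure to reproduce, because the sample size has no statistical basis and nothing is tested. The check has two parts.

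**1. Can any rule based on the listed fields place the severity correctly?**

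Take two hypothetical AEs, with HSCT on day 60:

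- A: starts mild on day 20, becomes severe on day 75, ends on day 90. It was severe only after HSCT.
- B: starts severe on day 20, eases to mild before HSCT, ends on day 90. It was severe only before HSCT.

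Under Protocol 6.5.5.1.3 both are stored identically: start day 20, end day 90, maximum severity SEVERE. Three possible assignment rules give:

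| Rule | Severe before HSCT? | Severe after HSCT? | Correct for A? | Correct for B? |
|---|---|---|---|---|
| Onset date (20 < 60) | yes | no | no: false before, absent after | yes |
| Overlap (20 < 60 and 90 ≥ 60) | yes | yes | no: false before | no: false after |
| End date (90 ≥ 60) | no | yes | yes | no: absent before, false after |

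The stored dates and grade are the same, so a rule that uses only these must treat A and B alike and be wrong for at least one. The false pre-HSCT severe count for A arises under the onset and overlap rules. Its absence after HSCT arises only under the onset rule.

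**2. How much does one such patient move the table?**

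Inputs: n = 10 to 18 treated patients (Protocol 6.1.1), and the all treated analysis set for all safety analyses (SAP 6.10). Shift per patient = 100 / n.

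- n = 10: 100 / 10 = 10.0 percentage points.
- n = 18: 100 / 18 = 5.6 percentage points.

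This applies at subject level and only if the patient has no other severe AE before HSCT. A patient who has one is already in the row. The severe related row moves by the same amount if the event was judged related and the patient has no other severe related AE before HSCT.

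If the post-HSCT percentages were instead based on transplanted patients (an assumption; the SAP does not say so), the 70% of treatment-experienced patients who proceeded to transplantation in the earlier study (Protocol 4.1.1.3.2) would give:

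- 0.70 × 10 = 7 patients: 100 / 7 = 14.3 points.
- 0.70 × 18 = 12.6, about 13 patients: 100 / 13 = 7.7 points.

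**The case against.** **The SAP does not say that the split uses onset date.** This stands. Its start-date rule is about treatment emergence relative to first infusion, not about HSCT. A reader might infer that the plan as written counts these AEs as severe before HSCT and drops them afterwards. That is the likely result of an unstated rule, not a stated one. The gap remains all the same, because overlap and end-date rules on the same fields also misplace severity.

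**The eCRF instructions may already deal with changes in an ongoing AE.** They may, and so may the table shells and dataset specifications that the SAP cites; none can be seen here. But the protocol text says that only the worst intensity is reported, and the SAP, written against CRF version 1.0, lists one maximum severity. If the instructions do ask for dated changes, the protocol and SAP should say so.

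**A post-transplant problem may be recorded as a new AE.** Protocol 6.5.5.1.3 prefers a diagnosis to single signs and symptoms, so a cytopenia or infection with a new cause may get its own record. This limits the point to worsening treated as the same event.

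**The protocol might seem to contradict itself**, since for screening-period events it says: "If it worsens after IMP initiation or during the follow-up period, an AE form must be entered with the appropriated intensity". It does not. Those events count as medical history and have no AE record yet, so worsening after first dose creates their first one. The rule is a useful model for the fix, not evidence of inconsistency.

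**The stakes are limited.** This is fair. The split is descriptive, and with 10 to 18 patients every AE is listed. The listings would identify AEs that span HSCT, though the listed fields would not show when they became severe.

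**Conclusion.** The concern holds in a bounded form. The plan keeps only the worst intensity of each AE up to EOS, lists no date of worsening, and still tabulates severe and severe related treatment-emergent AEs by period without a rule for AEs that span HSCT. Those rows cannot be relied on for spanning AEs. Under onset-date assignment, post-transplant worsening of an AE that began on emapalumab is counted as severe before HSCT and is absent afterwards; under an overlap rule the false pre-HSCT count remains.

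The size is 5.6 to 10.0 points per affected patient in the pre-HSCT severe percentage, on the all-treated denominator and for patients with no other severe AE before HSCT. A reader might try to turn this into an expected number of patients. The documents do not support that: they give no frequency of AEs that are ongoing at transplant and later become severe. The 79.4% in Protocol 4.3.1 is survival to HSCT, not the share transplanted.

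Only the severity rows of the split by HSCT are affected. The primary endpoint, overall AE and SAE incidence, and the whole-study maximum-severity tables are not. It is worth correcting before the tables are produced, but it does not threaten the main result.

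**What to change.** 1. **Recording.** In Protocol 6.5.5.1.3 and the eCRF instructions, reconciled with 6.5.5.1.5: when an AE that began earlier worsens after the transplant boundary, record the date of worsening, or open a new linked record with its own intensity, seriousness and causality. Count linked records once in whole-study event totals.
2. **Assignment.** In SAP 6.10.1, state that the split is by onset date, and use one boundary (HSCT or start of conditioning) throughout.
3. **Data already collected.** Using the existing start and end dates, show AEs that began before the boundary and ended after it, or were ongoing at it, in a separate row by maximum severity, with a listing. Report the pre-HSCT severe count both with and without them. If only the timing of severity is uncertain, the true count lies between the two. Simply removing spanning AEs would hide events that were already severe on emapalumab, like record B above.

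The cost is guidance text, SAP wording, a few extra AE records, and one extra table row and listing. The retrospective part needs no new data.

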6.5.5.1.4 Serious adverse event (SAE) and non-serious related AE reporting

Both serious and non-serious AEs are to be reported on the AE page of the CRF in English as specified in the CRF instructions and the investigator must assess the causal relationship of the event to study treatment.

The Sobi Global Pharmacovigilance & Patient Safety (GPV) department is to be notified by e-mail to [REDACTED] using the designated SAE reporting form / non-serious related AE reporting form, within 24 hours of the investigator's first knowledge of the following events:

- All SAEs (whether or not considered by the investigator to be related to study treatment)
- All non-serious related AEs (all non-serious AEs considered by the investigator to be related to study treatment)

The SAE reporting form/non-serious related AE reporting form is not always the same as the adverse event eCRF form. The forms must be completed in a consistent manner. For example, the same AE term should be used on both forms. The investigator must assess the causal relationship of the event to IMP and sign the report.

If the patient is hospitalized in a hospital other than the study site, it is the investigator's responsibility to contact this hospital to obtain all SAE relevant information and documentation.

All new information obtained, relevant to an SAE and/or a non-serious related Aereport, should be forwarded to Sobi within the same timeframe as the initial information.

The investigator shall provide Sobi with sufficient information to enable a complete medical assessment of the reported event. Best efforts shall be made by the investigator to provide Sobi with additional information related to any SAE and/or a non-serious related AE as requested.

Prompt notification by the Investigator to the Sponsor of SAEs and non-serious related AEs is essential so that legal obligations and ethical responsibilities towards the safety of participants and the safety of a study intervention under clinical investigation are met.

- An investigator who receives an investigator safety report describing a SAE or other specific safety information (e.g., summary or listing of SAEs) from the Sponsor, will review it and will notify the IECs/IRBs, if appropriate according to local requirements.
- Investigator safety reports must be prepared for SUSARs according to local regulatory requirements and Sponsor policy, and forwarded to investigators as necessary.
- The reference safety document to assess expectedness of a suspect serious adverse reaction and for reporting by the sponsor to Health Authorities, IECs/IRBs and investigators is the reference safety information section of the current version of the IB.

6.5.5.1.5 Follow-up of unresolved adverse events

All serious and non-serious AEs assessed by the investigator as related to the IMP should be followed until they are resolved or the investigator assesses them as chronic or stable, or the patient's participation in the study ends, i.e., until the EOS visit. How to report changes in an ongoing AE during a patient's participation in the study is described in the eCRF instructions.

In addition, all serious and non-serious AEs assessed by the investigator as related to the IMP should continue to be followed until they resolve or until the investigator assesses them as "chronic" or "stable", even after the patient's participation in the study is over, but without further recordings into the eCRF.

6.5.5.1.6 Exposure during pregnancy and breastfeeding

All events of exposure to the IMP during pregnancy (female patient or male patient's partner) or breastfeeding, shall be reported to Sobi Global Pharmacovigilance & Patient Safety by e-mail to [REDACTED] within 24 hours of awareness by any study personnel, whether the exposure is associated with an AE or not. This includes all situations where a female is or has been found to be pregnant after being exposed to IMP; directly, indirectly or via her partner (paternal exposure).

In all reported situations of exposure during pregnancy, Sobi will provide the investigator with a Pregnancy report form which shall be completed and returned by the investigator. The investigator is responsible for monitoring the outcome of the pregnancy and to inform Sobi of relevant information and any information requested related to the outcome of the pregnancy.

Any AEs and SAEs observed during and in relation to pregnancy, delivery or breastfeeding should be recorded in the eCRF and as applicable be reported to Sobi as described previously in this section.

6.5.5.2 Safety endpoint assessment

Number of patients who permanently discontinued study drug due to emapalumab-related adverse events. Occurrence and type of emapalumab-related adverse event as assessed by the investigator. Management and reporting of AEs related to these functions is described in Section 6.5.5.1.

The definitions of AEs related to the respective area above will be based on MedDRA System Organ Class (SOC) terms, High-Level Group Term (HLGT), High-Level Term (HLT), Preferred Terms (PT), and Standardized MedDRA Queries (SMQ).

6.5.6 Clinical safety assessments

6.5.6.1 Vital signs

Vital signs (body temperature, heart rate, and systolic/diastolic BP and oxygen saturation) will be measured at every visit and recorded in the eCRF.

BP should be measured in the same body position consistently throughout the study, if possible.

Temperature is to be measured pre-infusion, at the end of the infusion, 1 hour and 2 hours after the end of each infusion.

For the first infusion (or the first infusion after an increased dose) BP and heart rate will be measured every 15 minutes during the infusion, at the end of infusion and 1 and 2 hr. post-infusion. Oxygen saturation will be measured continuously during the infusion and up to 2 hr. post-infusion.

For subsequent visits, if no infusion-related reactions have occurred, BP, heart rate and oxygen saturation will be measured every 30 minutes, at the end of infusion and 1 and 2 hr. post-infusion.

Following windows can be applied to the vital signs measurement:

- When measured every 15 minutes: ± 5 minutes
- When measured every 30 minutes: ± 10 minutes
- When measured at 1 hour and 2 hours after infusion: ± 15 minutes

Clinically significant abnormal vital signs should be reported as AEs (see Section 6.5.5.1.1 for details).

6.5.6.2 Height and weight

Body weight (in kg) will be recorded at each visit during the treatment period, at the EOT visit, and at the final 1-year visit during the follow-up period (EOS)/discontinuation visit. Height (in cm) will be recorded at screening, at the EOT visit, and at the EOS/discontinuation visit. For patients older than 18 years of age height is only recorded at enrollment visit.

6.5.6.3 Physical examination

A complete physical examination will be performed at screening and a brief examination (including spleen and liver size (by abdominal palpation) general appearance of the skin and neurological status) at all other visits indicated in the schedule of assessments, see Table 3 and Table 4. Information for all physical examinations must be included in source data and will not be recorded in the database.

Each component will be recorded in eCRF as “normal” or “abnormal” at each visit. Abnormalities should be described, and clinical significance assessed.

If any abnormalities are reported at baseline they should be recorded as medical history. New or worsening of abnormalities should be reported as AEs if clinically significant (see Section 6.5.5.1.1 for details).

6.5.6.4 Electrocardiogram

A 12-lead ECG recording will be performed at screening, at the 8 weeks visit, and EOT. The ECG assessments will be performed locally at site and will be reported as “normal” or “abnormal” in the eCRF. Any abnormalities should be specified, and clinical significance assessed. ECGs assessed as abnormal should be assessed by an investigator with experience of assessing ECGs in children at different ages. Abnormalities reported at screening should be recorded as medical history.

Clinically significant abnormal ECG findings should be reported as AEs (see Section 6.5.5.1 for details).

